Participants will all be told what the goals of the study are: We want them to lose 16 pounds in 16 weeks and keep the 16 pounds off for another 16 weeks. From week 16 to week 32 we want them to at least maintain their weight loss. When the participant enters their weight into the portal, a new goal weight will be generated. The weight goals will be re-calibrated every month based off the participant's entries. Weight loss goals will be capped at a maximum of 4 pounds. If the participant reaches a point where they must lose more than 4 pounds in a week the goal remains a maximum of 4 pounds for the next week. If the participant reaches a point where they must lose more than 4 pounds a week to reach the 16-pound goal the rewards will be removed because we do not want to incentivize unhealthy or safe behaviors. If a participant loses 10 pounds or more in a week they will be contacted by a study staff member (coordinator ([name], [name], [name] or [name]), PI ([name]) or physician ([name] or [name]) to ensure they are using an appropriate weight loss method. The participant will also be asked of any illness or new medical treatments. Participants that are within .4 pounds of the goal will receive the reward if they are in the financial or non-financial groups. Participants within the financial or non-financial rewards group will earn \$25 (or equivalent non-financial reward) for every successful monthly weigh-in. This occurs at weeks 4,8,12 and 16. Participants in these groups will have the opportunity to randomly win \$100 (or point equivalent for non-financial rewards) at three random times for successful weigh-ins at their goal weight ( $\pm .4$  pounds). During weeks 16-32, participants in the two rewards groups will be eligible for a token reward just for entering their weight.

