In order to ameliorate the effects of habituation to the reward as Jeffery (2012) suggests, we will improve the perceived odds of winning to a 1-in-4 chance over weeks 8-16. For each patient, we will use a random number generator to randomly sort numbers from 1 to 8 and pick the top two listed numbers as the two weeks on which the patient will receive \$100 for an on-target weight. Veterans who meet all weekly targets will receive \$100 in guaranteed rewards, and \$300 in random rewards, for a total expected earnings of \$400 (average of \$100/month), used in the JAMA, JGIM, and Annals studies described in Table 1. If a patient misses a monthly weight target, their weekly target weight for the remainder of the reward period will be recalibrated so that the patient can still earn rewards if the patient's weight loss trajectory puts them on track to lose 16 lbs. in 16 weeks, if the weight loss does not exceed 4 lbs. per week.

Once the participant completes his/her weight entry in the portal they will immediately be told if they won their reward or not. If the patient withdraws they will receive what they have earned up to that point in time and we will ask them to participate in an interview to better understand why this study didn't work for them. For participants in the financial reward group, they will receive a check in the mail for their reward. Receipt of the check can take between 3-12 weeks. Depending on enrollment, we will either request the check be issued within one week of when it was earned and the participant is notified or we will submit a request at 16 weeks for the participant to be paid then. To collect the reward, we will ask that the patient come to the clinic for an in-person weigh-in with study staff, but we cannot require it. They will receive the reward regardless of their in-person weight. We do this in part because weight can fluctuate throughout the day and because the true test of whether rewards work will be determined at the 16 and 32 week in-person weigh-ins. Knowing there will be a

weigh-in prior to collecting the reward may also reduce the under-reporting of weight. Participants may login to the portal at any time and see how much they have earned (financial or non-financial).

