Potential risks from study participation may include breach of PHI, stigma from being associated with a weight management research study, stress due to trying to reach the study goals, and in some patients, unhealthy behaviors to reach study goals. Precautions have been put in place to minimize these risks.

The Principal Investigator and co-Investigators will review any critical incidents (death or hospitalization). [name], a practicing nephrologist and health services researcher, and [name] will evaluate the potential for causal relations between the incident and study interventions. Adverse events will immediately be reported to the participants care provider, project manager/coordinators, IRB and research compliance staff. [name] and [name] will be available to meet with any providers or patients to discuss concerns. The participants will bear no financial risk from any adverse effects of encounters from the study.

Several steps will be taken to minimize the risk of invasion of privacy. Initial contact with prospective participants will be made via an introductory letter with a stamped return post card allowing her/him to opt out of further contact by the study team, thus limiting risk for invasion of privacy. Several steps will be taken to ensure confidentiality and data protection throughout the rest of the study. All data gathered at the enrollment visit (the surveys, weigh-ins, health goals) and subsequent information will be confidential and will be housed on secure password protected VA servers. Data will be kept in offices at VA Puget Sound HSR&D with locked filing cabinets and password protected computers. The investigators, project coordinators and data analysts will be the only staff to have access to confidential records. Data collection, storage and management for this research project will adhere to all applicable VA policies, the VA Puget Sound Health Care System's Automated Information Systems Security Policy, and the established Data Security Policy of the Seattle HSR&D. Access will be restricted to study investigators, the study data analyst, research coordinators and the HSR&D Center data manager. Protected health information will not be disclosed, copied, transmitted by email, or transmitted in total or in part to anyone not connected with the approved protocol and not approved by the VA (via a Data Use Agreement, if necessary) to access the identifiers.

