If the participant doesn't complete the baseline survey within four weeks of their baseline study visit, they will be withdrawn from the study. Prior to being withdrawn, we will make up to three attempts to contact them. Depending on what study arm the participant is in, the participant will be compensated for their participation up to the point where they stopped participating.

**5.8.c. Medical withdraw.** If a participant loses more than 10 pounds in one week the research staff will discuss the participants' weight loss strategy with them. The physician researchers, [name] [name] or [name] will also review their chart to determine if there is medical condition that would contra-indicate further participation. If the participant is engaging in unhealthy methods of weight loss they will be counseled against these methods, referred to their primary care provider, and the MOVE! workbook methodologies will be reiterated. The participants will also be told that if a clinician determines their weight loss exceeds healthy limits, they may be withdrawn from the study. If the participant discloses their pregnancy or the study team finds out they are pregnant they will not be able to continue in the study. If this occurs the same withdraw procedures will be followed for active withdraw. Participants will be compensated for all activities earned to the date of withdraw as outlined in the informed consent document.

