## 6.0 Reporting

We do not anticipate any serious adverse events during this study. All unanticipated serious adverse event(s) or problem(s) will be reported to the IRB within 5 business days of becoming aware of the event. Serious adverse events, anticipated problems, non-serious protocol deviations, non-serious problems will all be reported to the IRB on the Continuing Review or project termination. As required by Handbook 1058.1 the adverse event rate (injuries) will be reported to the Office of Research Oversight quarterly by the Principal Investigator.

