### 6.3 Safety Review Plan

Study progress and safety will be reviewed monthly (and more frequently if needed). Patient weight loss will be closely monitored and if weight loss occurs at a rate of more than 5 pounds per week, a clinical review will be

completed. An annual report will be compiled and will include a list and summarization of adverse events. In addition, the annual report will address (1) whether adverse event rates are consistent with pre-study assumptions; (2) reason for dropouts from the study; (3) whether all participants met entry criteria; (4) whether continuation of the study is justified on the basis that additional data are needed to accomplish the stated aims of the study; and (5) conditions whereby the study might be terminated prematurely.

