### 9.1 Types of Data

#### 9.1.a. Participant data for recruitment.

Potential participants' names, contact information and healthcare data will be obtained from VistA, CPRS, CDW, and/or VSSC. This data will be stored electronically on secure VA servers within the VA HSR&D COIN in Seattle and/or within a VINCI workspace.

**9.1.b Participant data during study visits.** Data recorded during study visits will be identified only by subject ID and will include weight, reward given/level earned and anything the participants notes (Appendix I). This information will be housed on the secure VA server. This information will then be entered directly into a secure access database located on the secure research drive on VA servers within the HSR&D COIN in Seattle. Participants will complete the surveys in the portal. Survey responses will be downloaded to the secure J:drive folder where they will then be matched with participant information. All survey data will be recorded in a secured password protected database located on the secured VA HSR&D COIN researcher server in Seattle.

**9.1.c. Participant weights recorded in the portal.** Participants will be asked to report their weight every week on a pre-determined day they selected. They will login and enter their weight. All weights will be recorded by the portal and then sent directly to the secure J:drive folder located the VA HSR&D COIN network in Seattle.

**9.1.d Weights obtained via wireless scales.** Coordinators and project staff will discuss the wireless scales and data collection with participants prior to use. Participants in this arm will be given the wireless scale and a wireless router Connect device. Participants will need to plug Connect in within 50 feet of the scale. Every time the scale is activated the weight is automatically sent via the wireless router to the company server. The company will then send weights to the Principal Investigator through a standard secure socket shell (SSH) connection. Weights will be recorded in the study database located on a secure VA HSR&D server.

A subset of the study participants will receive Blipcare scales and Connect devices. Blipcare provides wireless digital scales with Bluetooth connection to a cellular device. The cellular device transmits the information from the scale to servers at Blipcare via the cellular network hotspot, thereby avoiding the use of the Veteran's own Wifi and/or smartphone and consequent charges to transmit data.

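### No routine, arm-neutral method of finding adverse events is described; outside the scheduled surveys, the one explicit illness question follows rapid weight loss

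*Combined protocol and SAP*

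**What the plan says.** Three provisions commit the study to safety outputs. Section 5.1.b: "The Principal Investigator and co-Investigators will review any critical incidents (death or hospitalization"). Section 6.0: "the adverse event rate (injuries) will be reported to the Office of Research Oversight quarterly by the Principal Investigator". Section 6.3 adds a monthly safety review and an annual report that judges whether adverse event rates match pre-study assumptions. The available text does not state those assumptions.

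The procedures that could find events are these:

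- Section 5.1.a: "If a participant loses 10 pounds or more in a week they will be contacted by a study staff member", and at that contact "The participant will also be asked of any illness or new medical treatments".
- The medical-withdrawal paragraph (numbered 5.8.c, within section 5.7): "If a participant loses more than 10 pounds in one week the research staff will discuss the participants' weight loss strategy with them". A physician chart review follows.
- Section 6.3: "if weight loss occurs at a rate of more than 5 pounds per week, a clinical review will be" completed.
- Section 9.1.b: the data recorded at study visits "will include weight, reward given/level earned and anything the participants notes (Appendix I"). Section 5.5.c describes the visit measurement as a weighing.
- Sections 5.5.b and 5.1.b: all arms complete a survey at baseline, 16 weeks, 32 weeks and 1 year. It includes SF12 health status and the PHQ-8, and section 5.1.b says it contains health history questionnaires.

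**The concern.** A count of adverse events is only as good as the method of finding them. If people are asked mainly when they lose weight fast, detection is tied to the outcome that the rewards are meant to change. If other events surface only when someone mentions them, counts run low, and lowest for people who have stopped attending. The figures at stake are the incident reviews, the quarterly rate and the annual judgement on rates. Harm is not a remote idea here: section 5.1.b itself names unhealthy behaviour to reach study goals as a risk.

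**Working it through.** The plan gives no adverse event rate, so there is no figure to reproduce. The check is a comparison of provisions, followed by two illustrations.

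**1. Promised outputs against described sources**

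- *Deaths and hospitalisations.* These are to be reviewed (5.1.b), but no section says how the investigators learn of them. The medical record is used to recruit, to collect weights (5.2.b), to impute missing weights (5.6.a) and to review charts after rapid weight loss (section 5.7). No routine search for admissions or deaths is described.
- *Adverse event rate, with injuries in brackets.* It is to be reported quarterly (6.0), but no definition of an adverse event and no standard question about injury appears.
- *Survey.* It is scheduled and the same in every arm, so health is asked about independently of weight loss. But the components in section 5.5.b are mainly status and behaviour scales, and none is described as recording admissions or injuries. No section routes survey answers to the safety review, and questions may be skipped.
- *Active checks.* All three depend on weight loss: 10 lb or more in a week, more than 10 lb in a week, and more than 5 lb per week. They may be meant as tiers, but the text does not say so, and the actions attached to them differ.

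**2. How much could the weight trigger differ by arm?**

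Table 1 gives planning values at the end of rewards of 1.6 lb lost in usual care and 8.1 lb in each reward arm. Mean weekly losses are therefore 1.6/16 = 0.10 lb and 8.1/16 = 0.51 lb. The SD of weekly change is not given, so 2 to 5 lb is assumed, with normal and independent weeks. The weekly chance of a trigger is p = 1 − Φ((threshold − mean)/SD), and the chance of at least one in 16 weeks is 1 − (1 − p)^16.

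For example, with a 10 lb threshold and SD 3, p is 0.000483 in usual care and 0.000777 in a reward arm. The 16-week chances are 0.8% and 1.2%.

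| Weekly SD (assumed) | 10 lb, usual care | 10 lb, reward | 5 lb, usual care | 5 lb, reward |
|---|---|---|---|---|
| 2 lb | 0.001% | 0.002% | 10.8% | 18.0% |
| 3 lb | 0.8% | 1.2% | 56.9% | 67.1% |
| 4 lb | 10.1% | 13.2% | 84.6% | 89.4% |
| 5 lb | 32.0% | 37.3% | 94.3% | 96.2% |

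The direction is as expected. For the illness question (10 lb), the largest gap is 37.3 − 32.0 = 5.3 percentage points. The ratio falls from 1.6 at SD 3 to 1.2 at SD 5. At SD 3 or below, almost nobody in any arm would be asked. For the 5 lb clinical review, the largest gap is 67.1 − 56.9 = 10.2 points, but the text does not say that this review asks about events.

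**3. How many events could sit among people lost?**

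Assume that 5% to 15% of participants are admitted once in the year (not from the documents). With 280 participants (5.2.a), 280 × 0.05 = 14 and 280 × 0.15 = 42 admissions. With the 20% loss in section 5.6.a, 14 × 0.20 = 2.8 and 42 × 0.20 = 8.4. With the 274 enrolled by March 2020 (5.1.c), the range is 2.7 to 8.2. This assumes the same admission rate in those lost, loss for the whole year, and no other route of discovery.

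**The case against.** The strongest objection is that absence is being read from incomplete papers. The visit record (Appendix I), the survey (Appendix C) and the phone-visit script were not available, and any of them could hold an event question. Section 9.1.b's wording on participants' notes is also ambiguous. This stands, so the point is limited to what the available text describes.

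A reader might infer that participants are asked about health only after rapid weight loss. The documents do not support that, because the surveys ask every arm about health on a fixed schedule.

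A reader might also infer that events are in fact found more readily in the reward arms. The trigger applies in all arms, and section 2 of the working shows a modest gap. Extra staff contact adds little that can be relied on. "To collect the reward, we will ask that the patient come to the clinic for an in-person weigh-in with study staff", but attendance cannot be required. Seven rewards (4 monthly plus 3 random) is a maximum, checks and non-financial rewards are mailed, and no collection visit is described as asking about health. In-person study visits stopped in March 2020. After week 16 only mailed tokens remain, so an admission at week 20, say, would be no less visible in usual care than in a reward arm. Calls after missed entries apply to every arm.

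Finally, no aim or hypothesis compares harms between arms, and the protocol describes minimal risk. That also stands, and it limits the consequence to the safety reporting. It does not supply the missing method for the rates the plan has undertaken to report.

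**Conclusion.** The point holds as a gap in safety ascertainment. The available text describes no routine, arm-neutral method of finding hospitalisations, deaths or injuries, and the active checks it does describe all start from weight loss. Events may be under-counted, chiefly among people lost to follow-up: about 3 to 8 admissions under the assumed 5-15% rate and the plan's 20% loss. A difference in detection between arms is plausible, but it is probably small and cannot be quantified without the SD of weekly weight change and the unseen forms. It would be going too far to say that the reported rates are known to be too low, or that the trial fails a safety comparison it never set out to make. Hypotheses 1a to 1c are unaffected. The change is worth making because it is cheap.

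**What to change.** 1. Ask all three arms one identical question about hospitalisation, illness and injury at the remaining 16-week, 32-week and 1-year visits, in person or by phone. If the unseen forms already contain one, cite it in the protocol.
2. State what counts as an adverse event.
3. Query CDW/CPRS for admissions and deaths through 12 months for every randomised participant, including those withdrawn or lost where authorisation permits, and retrospectively for visits already completed.
4. Tabulate events by randomised arm in the section 6.3 annual report, with weight-triggered reports shown separately so that they do not drive the rates.
5. Reconcile the weight-loss triggers in section 5.1.a, the medical-withdrawal paragraph and section 6.3. Which threshold or action should apply is for the study's clinicians to decide.

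The cost is one item in an existing visit script and a query of systems the team already uses for recruitment and weights. There will be more events to list and report. The new question cannot reach visits already completed, which the record query covers only in part, so the report should say which method found each event.

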### **5.1.c. Study population.**

We will approach approximately 5,000 patients with introductory letters. We will enroll and consent up to 350 patients. Our target enrollment is 280 Veterans total—80 in the no-reward arm, and 100 in each of the two reward arms. As of 3/6/2020 we have currently stopped enrolling. We have presently enrolled 274 participants. Once we have additional information about coronavirus to make an informed decision about recruitment we will either formal close enrollment at 274 or we will continue.

## **5.2 Recruitment Methods**

Please refer to study flowchart for a complete visual depiction of the study procedures.

**5.2.a Enrollment goals.** Our target enrollment is 280 Veterans total—approximately 80 in the usual care arm, and 100 in each of the two reward arms.

All potential study participants will be patients enrolled in primary care at VA Puget Sound Health Care System. Potential participants will be identified by querying the scheduling database, CDW, VistA and/or VSSC as explained below.

**5.2.b. Recruitment procedures.** Participant recruitment will occur by a study team member in the role of Principal Investigator ([name]), research coordinators ([name]/[name]/[name]/[name]), co-Investigators ([name]/[name]), or study clinician ([name]/[name]).

We will have a table during research week for recruitment. We will be giving potential participants a handout basic information about the study (Appendix AG). We will also have postcards (Appendix AH) that potential participants can complete with their name, phone number, date of birth and best time to call. These participants will be screened and then given a phone call. Potential participants that do not wish to leave their information can call the participant line and will follow all of the procedures as outlined below.

[name] has flyers that he can pass out to other VA primary care providers in order to give to primary care patients who may be eligible for the study.

In addition, we will have flyers that Veterans can give to interested family or friends who can call us to complete a phone screening. We will collect their full names and dates of birth in order to conduct a CPRS screen.

For all non-referred patients, using a waiver of informed consent and HIPAA authorization for recruitment purposes, we will query the VA Puget Sound scheduling database, CPRS, VistA, CDW and/or VSSC. We will include patients who fall within the following parameters: between 18 and 69 years of age, last recorded weight under 390 pounds, BMI greater than or equal to 30 and Veterans. We will exclude patients who have a behavioral flag, a diagnosis of an eating disorder, PTSD with sexual trauma, serious mental illness or on antipsychotic medication, participated in the MOVE! program in the past 4 months, or are pregnant, using insulin to treat diabetes, or a prisoner. Initial study eligibility will be determined with a combination of a CDW/VSSC/VistA data pull using the aforementioned inclusion/exclusion criteria and CPRS chart review if needed (see Section 5.4.a for detailed description and rationale for the exclusion criteria.) Access to these data sources requires access to real SSNs.

Weekly a list of potential participants will be generated in either CDW, VSSC, or VistA (using fileman). If using CDW the cohort will be generated by VINCI personnel and stored in the VINCI workspace. When the file is ready, either a copy of the data will be downloaded from the VINCI workspace to the secure J:drive study folder or our database will connect directly with the VINCI SQL tables. Patients who have "opted-out" will not be contacted again. For VistA, fileman will be used to query VistA to find patients who fall within the inclusion/exclusion parameters. For participants that do end up enrolling in the full study we will do a second pull to collect all of their weights recorded in CPRS for the previous five years.

Participants meeting the initial criteria will be sent a recruitment letter (Appendix J) and opt-out post card (Appendix K). If we do not receive the post-card back within a few weeks a study team member will call them, explain the study and invite them to participate. We will make up to five attempts to recruit potential participants. During this phone call, the study team member will ask the potential participant screening questions (see section 5.5). Under a waiver of documentation of informed consent and HIPAA authorization, if participants give verbal approval, we will retain their screening information regardless of their eligibility. If participants are deemed eligible, the study team member will set up a convenient time to meet them. We will make every effort to have this occur directly before or after their primary care or women's clinic appointment, if they have one. Participants are free to ask questions about the study or study procedures at any point, and are free to withdraw or refuse to participate in any aspect of the study without penalty.

At the in-person visit, potential participants will be consented (Appendix A) and asked to sign the HIPAA authorization form (Appendix B). After initial study evaluations are conducted, the participants account in the portal will become active, the coordinator will provide the participant with the website portal instructions, user name and password (Appendix S). All participants will use the portal to enter in their weekly weights and complete the four participant surveys (baseline, 16 and 32 weeks and one year). Participants will be

randomized to a study group (financial, non-financial or control) once they have completed the participant survey (see section 5.5 for details regarding study evaluations).

Because of the importance of women's health to the VA, we will oversample women to ensure that 25% of the sample (n=70; approximately the total number of participants in the JAMA 2008 or JGIM 2011 reward trials) will be women and then stratify by gender. To enroll 280 Veterans, we can recruit as few as 10 per month per site over 15 months. This is a similar recruitment rate to JAMA (2008) (12/month per site) and a recently funded clinical trial at VA Puget Sound Health Care System (Nelson IIR# 14-063: 390 Veterans over 24 months). By randomizing in blocks of 14 and recruiting at least 20 Veterans per month we ensure that treatment arms will be balanced in terms of the season of the year the participants entered the trial.

